## 1. Background/Significance:

Despite being identified in 1999 in '*To Err is Human*' as a central facet of patient safety, diagnostic errors (missed, delayed or incorrect diagnoses) remain understudied, cause appreciable patient harm, and their reduction lags behind advances in other patient safety areas.. Limited pediatric-focused research on diagnostic errors highlights the significance of this problem in children: 54% of pediatricians report making diagnostic errors at least monthly and 45% report making harmful diagnostic errors at least annually. In ambulatory pediatrics, evidence of harmful diagnostic errors is emerging: children experience a median delay of 3 years before receiving an asthma diagnosis, and 23% of children diagnosed with retinoblastoma have a diagnostic delay of more than 8 weeks, leaving them at increased risk of tumor invasion. Errors in diagnosis were the most prevalent error type in closed pediatric malpractice claims. Evidence from adult and pediatric primary care settings suggest diagnostic errors are harmful and involve a variety of diseases.

Few studies rigorously investigate diagnostic error reduction efforts and even fewer focus on children. A recent review led by a co-investigator of this proposal, suggests a need for empirical studies to test interventions to reduce diagnostic errors, and that most existing studies focus on adults, lack rigorous process and outcome measures, suffer from non-experimental or quasi experimental designs, and/or were limited to a single institution. Evidence for reducing pediatric diagnostic errors is rare and often not current: the implementation of a pediatric trauma team reduced delayed and missed diagnoses of major injuries from 4.3% to 0.46%. Computer aided differential diagnoses reduced mean time to diagnosis of all pediatric inpatients from 2.8 days to 1.9 days in 1975. Research on interventions to prevent pediatric diagnostic errors is needed.

The proposal will focus on 3 specific, high-risk, pediatric ambulatory diagnostic errors each representing a unique dimension of diagnostic assessment: evaluation of symptoms, evaluation of signs and follow-up of diagnostic tests. Adolescent depression (i.e. symptoms) affects nearly 10% of teenagers, is misdiagnosed in almost 75% of adolescents and causes significant morbidity. Pediatric elevated blood pressure (signs) is misdiagnosed in 74-87% of patients, often due to inaccurate application of blood pressure parameters that change based on age, gender and height. Actionable pediatric laboratory values (diagnostic tests) are potentially delayed up to 26% of the time in preliminary investigations and 7-65% in adults, leading to harm and malpractice claims.

We propose to conduct a multisite, prospective, stepped wedge cluster randomized trial testing a quality improvement collaborative (QIC) intervention within the American Academy of Pediatrics' Quality Improvement Innovation Networks (QuIIN) to reduce the incidence of pediatric primary care diagnostic errors. QuIIN is a national network of over 300 primary care practices, ranging from tertiary care academic medical centers to single practitioner private practices, interested in and experienced with QICs. Because many processes are likely to be common across diagnostic errors in outpatient settings, a multifaceted intervention, such as a QIC, has a high likelihood of success and broad applicability across populations. Preparatory inquiries to QuIIN primary care providers suggest high interest in reducing these 3 diagnostic errors and provider agreement with randomization to evaluate diagnostic error interventions.

The purpose of this IRB application is to cover the data analysis of the QIC data generated in this project. The AAP's IRB will cover each individual pediatric clinic, the data collection and the conduct of the study.

#### 2. Study Design: Objectives:

# Primary

- To determine whether a QIC consisting of evidence-based best-practice methodologies, mini-root cause analyses, data sharing, and behavior change techniques, is associated with a reduction in 3 specific diagnostic error rates in a national group of pediatric primary care practices.
  - Hypothesis 1: Implementation of a QIC will lead to a 40% reduction in missed diagnosis of adolescent depression.
  - Hypothesis 2: Implementation of a QIC will lead to a 30% reduction in missed diagnosis of pediatric elevated blood pressure.
  - Hypothesis 3: Implementation of a QIC will lead to a 45% reduction in delayed diagnosis of actionable laboratory results.

## Secondary

- To determine if a QIC's effect changes for wave 1 versus wave 2 participants, who serve as the control group in the first year of the collaborative.
- To further investigate the epidemiology of three ambulatory pediatric diagnostic errors: missed diagnosis of adolescent depression, missed diagnosis of pediatric elevated blood pressure, and delayed diagnosis of actionable laboratory results.
- To evaluate patient outcomes related to these diagnoses including outcomes after positive depression screening, missed elevated blood pressure screening and delayed diagnosis of actionable laboratory values.

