# Methods:

This proposal aims to identify systems solutions for reducing harmful pediatric diagnostic errors. We will perform a prospective, stepped wedge cluster randomized controlled trial to test the hypothesis that QIC strategies can reduce three specific diagnostic errors in a national group of ambulatory pediatric primary care practices. These data will inform future diagnostic errors. Baseline data from the QIC will identify incidence data for errors in 3 separate stages of the diagnostic process: symptoms (missed diagnosis of adolescent depression), signs (missed diagnosis of pediatric elevated blood pressure) and diagnostic tests (delayed diagnosis of actionable laboratory results). Each of these diagnostic errors represents missed opportunities to recognize abnormal diagnostic findings. Human subjects' protection will be completed at the CHAM to cover the researchers and data analysis and at the American Academy of Pediatrics to cover all practices, as completed for prior QuIIN projects.

The goal of this proposal is to reduce diagnostic errors by tracking diagnostic errors rates (outcomes measures) and reliably performing best practices for diagnosing adolescent depression, pediatric elevated blood pressure and actionable laboratory results (process measures). In order to reduce overall data collection burden on practices and to increase engagement of practices that would have been in the control group, we have changed the study design. These changes do not affect the statistical power of the study. The intervention will consist of implementing QIC methodology in all practices to assist teams in reliably performing the processes that will reduce the diagnostic error outcomes via evidence-based tools. Practices will be randomized into three groups, with each group intervening on 1 diagnostic error and serving as the control group for a second diagnostic error. After 8 months of participation, each group will begin intervening on the diagnostic error they were a control group for, continue intervening on their original diagnostic error, and function as the control group for the third diagnostic errors. In the final 8 months of the QIC, all three groups will intervene on all three diagnostic errors.

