All practices will participate in the QIC for the full 2 years of the study. They will attend an initial 2-day interactive webinar learning session where they will learn QI methodology. enhance and practice QI skills, identify local 30-60 day aims for the diagnostic error they are intervening on first, increase their understanding of diagnostic errors and these errors in particular, and create systems for standardized data collection and data entry. Practices will submit monthly data on their intervention and control diagnostic errors but only receive centralized data feedback, coaching or collaborative involvement regarding their intervention error. (Figure 1) We acknowledge that error measurement in the baseline and intervention periods may introduce an intervention effect, but we have no reason to believe this effect will be different for the intervention and control practices. As noted above, after 8 months, practices will participate in a second 2-day video conference learning session, continue to intervene on their first error, begin to intervene on the error they were a control group for and begin to collect control data for the third diagnostic error. Including the control group in the QIC ensures that harm is prevented in the maximum number of patients and that clinical equipoise is met, as we believe this intervention will reduce errors. This stepped wedge design with two steps allows for the primary outcome comparison (diagnostic errors in intervention versus control) and secondary outcome comparisons: 1) diagnostic error rates in second wave participants), 2) Sustainability after first eight months and 3) collaborative effect for second wave practices. These secondary outcome comparisons will shed light on the effectiveness and sustainability of QICs and inform future collaborative designs.

Given concerns about practice attrition, we will additionally recruit a second wave of practices to join the collaborative. The three phase quality improvement research model lends itself to simply on-boarding a new group of practices and integrating them into the project in Phase 2 which would begin in June of 2016. The up to 15 Wave 2 practices would be recruited

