in the winter of 2015-2016, similarly randomized to the three already established collaborative groups and enrolled in March of 2016, collect baseline data comparable to the wave 1 practices and then participate in the collaborative beginning in June of 2016. As noted above, after 8 months, practices will participate in a second 2-day video conference learning session, continue to intervene on their first error, begin to intervene on the error they were a control group for and begin to collect control data for the third diagnostic error. The only difference between the Wave 1 and Wave 2 practices, are that the Wave 1 practices will ultimately intervene on all three diagnostic errors of interest. As the Wave 2 practices are entering the collaborative 8 months later, they will only intervene on two of the three diagnostic errors of interest over the course of 16 months. At the end of the collaborative, all resources and tools for the third diagnostic error will be given to the Wave 2 participants.

Target Diagnostic Error Outcome Measures:

All outcome metrics are described in detail in Table 2 and the Data Collection section below.

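### The first secondary objective makes Wave 2 the first-year control group, which the current design rules out, and the model for the wave comparison lists no phase or wave term

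*Combined protocol and SAP*

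**What the plan says.** Section 2, under Secondary objectives, sets out to learn whether the QIC's effect changes for "wave 1 versus wave 2 participants, who serve as the control group in the first year of the collaborative".

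The Methods text of the same section describes a different design. Three groups are randomized, "with each group intervening on 1 diagnostic error and serving as the control group for a second diagnostic error". After 8 months each group starts work on its control error and becomes control for the third. In the last 8 months all three groups intervene on all three errors. The text says the design was changed and leaves no stand-alone control group.

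Wave 2 appears later in Methods, with a different purpose: "Given concerns about practice attrition, we will additionally recruit a second wave of practices to join the collaborative". These practices are to be "similarly randomized to the three already established collaborative groups and enrolled in March of 2016". They "collect baseline data comparable to the wave 1 practices and then participate in the collaborative beginning in June of 2016". The plan speaks of "integrating them into the project in Phase 2 which would begin in June of 2016". On the scope of their work it states that "they will only intervene on two of the three diagnostic errors of interest over the course of 16 months". The reason it gives is their late start: "As the Wave 2 practices are entering the collaborative 8 months later".

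The Statistical Models paragraph in section 7 uses mixed-effects logistic models for both primary and secondary hypotheses. It names assignment, a random clinic intercept and a list of practice-level covariates. No calendar time, phase or wave term is listed.

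**The concern.** The objective and the design disagree about who the controls are. An analyst who follows the objective literally would look for first-year control data from Wave 2. For the first 8 months there are no monthly data from Wave 2 at all. In the remaining 4 months of that year Wave 2 practices are in both conditions, on different errors.

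The likely response is to pool phases and put wave into the model described in section 7. Wave 2 is observed only in the later part of the study. Without a term for calendar phase, any general change in error rates over the two years can then appear as a difference between waves. The plan means to use these secondary comparisons to judge the effectiveness and sustainability of such collaboratives and to inform the design of future ones.

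**Working it through.** **Timeline.** The QIC lasts 24 months in three 8-month phases, and Wave 2 enters 8 months late. So 24 − 8 = 16 months, and 16 / 8 = 2 phases, hence two errors. This reproduces the plan's own figures for Wave 2. Counting back 8 months from June 2016 puts the Wave 1 start at about October 2015 (derived, not stated).

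**Schedule for any one error.** From the Methods text, with I = intervention, C = control, – = no monthly data on that error:

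| Wave, and the error's place in the group's sequence | Phase 1 (months 1–8) | Phase 2 (9–16) | Phase 3 (17–24) |
|---|---|---|---|
| Wave 1, first | I | I | I |
| Wave 1, second | C | I | I |
| Wave 1, third | – | C | I |
| Wave 2, first | – | I | I |
| Wave 2, second | – | C | I |
| Wave 2, third | – | – | C |

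**Practice-months per error.** Take 25 retained Wave 1 practices and 15 Wave 2 practices (section 5), in equal thirds: 25/3 = 8.33 and 15/3 = 5 per group.

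- Months 1–8. Wave 1: 8.33 × 8 = 66.7 control and 66.7 intervention. Wave 2: 0 and 0.
- Months 1–12. Wave 1 control: 66.7 + 8.33 × 4 = 100. Wave 1 intervention: 66.7 + 2 × 8.33 × 4 = 133.3. Wave 2: 5 × 4 = 20 control and 20 intervention.

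Wave 2 therefore supplies at most 20 of 120 first-year control practice-months per error, all in months 9–12, with an equal number under intervention.

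**What can be estimated.**

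- Phase 1 alone, with intercept, wave, intervention and intervention × wave: the wave and interaction columns are all zero, so the rank is 2 of 4. No wave contrast exists.
- Whole study, with intercept, two phase terms, wave, intervention and intervention × wave: rank 6 of 6. The wave difference in effect can be estimated.
- Time in the collaborative equals calendar phase minus an indicator for Wave 2. A model with intercept, calendar phase, wave and time in the collaborative has rank 3 of 4. Adding the interactions of intervention with wave, calendar time and time in the collaborative to the six-term model gives rank 7 of 8. No model can separate all three.

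**Drift with zero true effect.** Let the outcome equal the phase number (1, 2, 3) in every cell and fit wave, intervention and their product with no phase term. The fit then reproduces the cell means:

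- Wave 1 control: (1 + 2)/2 = 1.5. Wave 1 intervention: (1 + 2 + 3 + 2 + 3 + 3)/6 = 2.33. Difference 0.83.
- Wave 2 control: (2 + 3)/2 = 2.5. Wave 2 intervention: (2 + 3 + 3)/3 = 2.67. Difference 0.17.
- Apparent wave difference among controls: 2.5 − 1.5 = +1.0. Apparent intervention × wave term: 0.17 − 0.83 = −0.67.

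With phase terms added, the wave, intervention and interaction terms are all 0. The calculation uses least squares on equally weighted cells and a linear scale. It shows the mechanism and does not forecast the bias in the trial's logistic model.

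**Which phases to use.** Wave 1 has no controls in Phase 3. Its control practice-months are 66.7 in Phase 1 and 66.7 in Phase 2. Restricting the comparison to Phases 2 and 3 would discard 66.7 / 133.3 = 50% of them, together with Wave 1's Phase 1 randomized contrast.

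**The case against.** The best defence is that the objective may use wave in another sense. In Methods, the secondary comparisons on second-wave participants and practices are presented as products of the two-step design, before the later recruits are introduced. There, and perhaps in the objective, second wave could mean the groups that start an error at the second step after serving as its control. The objective is then nearly coherent. The ambiguity is real and belongs in the fix. This reading does not rescue the wording, because those groups are controls for 8 months and not for a year, and the plan elsewhere uses Wave 2 for the added practices.

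A second defence concerns the model. Its covariates are introduced as examples, so a phase term is not forbidden, and contrasts made within a phase cancel a common additive drift. Both points are fair. The risk arises only when phases are pooled without a time term, but nothing in the plan prevents that.

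A reader might also infer more than the documents support:

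- **That Wave 2 is a non-randomized group without controls.** Its practices are randomized to the same three groups and have concurrent controls. Only membership of a wave is not randomized.
- **That no wave comparison can be made.** Only the control-group clause fails. The interaction is estimable.
- **That Wave 2 contributes nothing from the first 8 months.** Its one-time baseline may reach back, since baseline depression charts cover the preceding 6 months. That is not a monthly control series.

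**Conclusion.** The control-group clause conflicts with the current Methods text and should be corrected. On the documented schedule Wave 2 supplies no monthly data in months 1–8 and is never the year-one control group.

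The point goes beyond wording, because the model assigned to secondary hypotheses lists neither phase nor wave. A pooled wave contrast could then read a secular trend as a wave effect. The plan does not commit to that pooled analysis, so this is a risk left open and not a demonstrated bias.

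Even a correct model has a limit. At any calendar date Wave 1 has 8 more months in the collaborative, so a wave difference in effect cannot be given a causal reading.

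The practice-month counts assume equal thirds and no further attrition. The schedule assumes that Wave 2 groups begin with one intervention error and one control error, as the 16-month, two-error description implies. No primary hypothesis or power figure depends on the clause.

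**What to change.** 1. Delete the clause that makes Wave 2 the first-year control group.
2. State whether wave means the practices recruited later or the groups that start an error at the second step, and use the term in one sense throughout.
3. For the recruitment-wave objective, specify wave, calendar-phase and intervention-by-wave terms in the mixed-effects logistic model, and use data from all phases.
4. State that practices are randomized to groups within each wave, that wave membership is not randomized, and that wave is tied to time in the collaborative. Interpret any wave difference as descriptive.
5. If second-step and first-step starters within Wave 1 are also compared, state that this comparison too spans different calendar phases and different prior QIC experience, although the groups are randomized.

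The cost is some rewording, a few model terms and a more cautious interpretation of one secondary objective. No extra data are needed.

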# Methods:

This proposal aims to identify systems solutions for reducing harmful pediatric diagnostic errors. We will perform a prospective, stepped wedge cluster randomized controlled trial to test the hypothesis that QIC strategies can reduce three specific diagnostic errors in a national group of ambulatory pediatric primary care practices. These data will inform future diagnostic errors. Baseline data from the QIC will identify incidence data for errors in 3 separate stages of the diagnostic process: symptoms (missed diagnosis of adolescent depression), signs (missed diagnosis of pediatric elevated blood pressure) and diagnostic tests (delayed diagnosis of actionable laboratory results). Each of these diagnostic errors represents missed opportunities to recognize abnormal diagnostic findings. Human subjects' protection will be completed at the CHAM to cover the researchers and data analysis and at the American Academy of Pediatrics to cover all practices, as completed for prior QuIIN projects.

The goal of this proposal is to reduce diagnostic errors by tracking diagnostic errors rates (outcomes measures) and reliably performing best practices for diagnosing adolescent depression, pediatric elevated blood pressure and actionable laboratory results (process measures). In order to reduce overall data collection burden on practices and to increase engagement of practices that would have been in the control group, we have changed the study design. These changes do not affect the statistical power of the study. The intervention will consist of implementing QIC methodology in all practices to assist teams in reliably performing the processes that will reduce the diagnostic error outcomes via evidence-based tools. Practices will be randomized into three groups, with each group intervening on 1 diagnostic error and serving as the control group for a second diagnostic error. After 8 months of participation, each group will begin intervening on the diagnostic error they were a control group for, continue intervening on their original diagnostic error, and function as the control group for the third diagnostic errors. In the final 8 months of the QIC, all three groups will intervene on all three diagnostic errors.

The QIC intervention components are described in Table 1 and closely mirror prior evidence on components integral to QIC success and prior QICs conducted by QuIIN and the research team. Prior research by co-investigators and others have shown that reducing diagnostic errors requires more than just technological alerts, which is why a QIC intervention was chosen. The QIC will ensure the 6 key contextual MUSIQ factors will be met. increasing the ability of each practice to reduce these errors. Rapid data feedback on performance with benchmarking is crucial to behavior change for diagnostic error reduction. Root cause analyses have proven useful in identifying underlying causes of diagnostic errors. The mini-root cause analyses used in this QIC involve identifying 1 diagnostic error monthly at each QIC site, examining standardized patient, provider, and systems factors that could have led to the error, and spreading systematic lessons learned to prevent future errors. These factors could include 1) patient factors of age, gender, reason for visit, patient comorbidities, language barriers, acute illness, agitation of patient/family, social issues, etc., 2) provider factors of type of provider, provider level of training, provider fatigue/impairment, personal stressors of providers, provider disagreements, provider knowledge, provider beliefs about the project or the patient, etc. and 3) systems factors of time of visit, clinic milieu during visit (chaotic vs. calm), increased workload, staffing concerns, verbal/written communication, computer software or hardware, non-computer equipment, etc.. These deidentifed factors will be submitted to the QIC monthly in order to aggregate causes of these errors. No protected health information (PHI) will be collected in the aggregate entered data for these min-root cause analyses. One of the novel approaches of this collaborative is the use of an interactive webinar format for learning sessions.

All practices will participate in the QIC for the full 2 years of the study. They will attend an initial 2-day interactive webinar learning session where they will learn QI methodology. enhance and practice QI skills, identify local 30-60 day aims for the diagnostic error they are intervening on first, increase their understanding of diagnostic errors and these errors in particular, and create systems for standardized data collection and data entry. Practices will submit monthly data on their intervention and control diagnostic errors but only receive centralized data feedback, coaching or collaborative involvement regarding their intervention error. (Figure 1) We acknowledge that error measurement in the baseline and intervention periods may introduce an intervention effect, but we have no reason to believe this effect will be different for the intervention and control practices. As noted above, after 8 months, practices will participate in a second 2-day video conference learning session, continue to intervene on their first error, begin to intervene on the error they were a control group for and begin to collect control data for the third diagnostic error. Including the control group in the QIC ensures that harm is prevented in the maximum number of patients and that clinical equipoise is met, as we believe this intervention will reduce errors. This stepped wedge design with two steps allows for the primary outcome comparison (diagnostic errors in intervention versus control) and secondary outcome comparisons: 1) diagnostic error rates in second wave participants), 2) Sustainability after first eight months and 3) collaborative effect for second wave practices. These secondary outcome comparisons will shed light on the effectiveness and sustainability of QICs and inform future collaborative designs.

Given concerns about practice attrition, we will additionally recruit a second wave of practices to join the collaborative. The three phase quality improvement research model lends itself to simply on-boarding a new group of practices and integrating them into the project in Phase 2 which would begin in June of 2016. The up to 15 Wave 2 practices would be recruited

in the winter of 2015-2016, similarly randomized to the three already established collaborative groups and enrolled in March of 2016, collect baseline data comparable to the wave 1 practices and then participate in the collaborative beginning in June of 2016. As noted above, after 8 months, practices will participate in a second 2-day video conference learning session, continue to intervene on their first error, begin to intervene on the error they were a control group for and begin to collect control data for the third diagnostic error. The only difference between the Wave 1 and Wave 2 practices, are that the Wave 1 practices will ultimately intervene on all three diagnostic errors of interest. As the Wave 2 practices are entering the collaborative 8 months later, they will only intervene on two of the three diagnostic errors of interest over the course of 16 months. At the end of the collaborative, all resources and tools for the third diagnostic error will be given to the Wave 2 participants.

Target Diagnostic Error Outcome Measures:

All outcome metrics are described in detail in Table 2 and the Data Collection section below.

The missed diagnosis of adolescent depression primary outcome measure is defined as the incidence of depression in adolescents  $\geq$ 11 years old compared in intervention versus control practices. This outcome measure was chosen because prior research suggested up to 75% of adolescent cases are missed by primary providers, allowing incidence to serve as a proxy for missed diagnoses. The research team strongly considered using documented depressive symptoms (e.g. poor school performance, interrupted sleep patterns, increased disruptive behaviors, etc.) without appropriate provider identification or referral to mental health evaluation as the missed diagnosis of adolescent depression primary outcome. This metric was not chosen because preliminary data suggested the number of adolescents with symptoms suggestive of depression documented prior to a mental health referral was extremely small. This finding echoes research that pediatricians' use of adolescent and parental chief complaints to identify depressive risk factors consistently under identifies adolescent depression. The process measure for this diagnostic error will be the percent of adolescents screened for depression, a practice recommended for all adolescents by the USPSTF, and feasible and acceptable to primary care pediatricians.

 Table 2: Outcome and Process Measures, and Evidence-Based Tools for Diagnostic Error

 Reduction

Primary Outcome Measure	Process Measures	Evidence-Based Tools
Number of Adolescents Diagnosed with	1 Number of adolescents	1 Patient screening in the
Depression per 100 Adolescent Visits	screened for depression	waiting room
Patients >11 years old with documentation of	with the $PHO_9-M$ per total	2 Triage purse scoring and
major depression or subsyndromal depression	number of adolescents	flagging to facilitate
diagnoses	seen per month	provider recognition
Flevated Blood Pressure Not Recognized by	1 Number of patients >3	1 Triage nurse or FHR
Providers per 100 Elevated Blood Pressures	vears old with blood	flagging of elevated
Measured	pressure checked at triage	blood pressures to
Systolic or Diastolic Blood Pressure > 90 th	per total number of	facilitate provider
percentile for age, gender and height or $>120/80$	patients >3 years old seen	recognition
in >3 years old patients without history of		2. Family notification of
hypertension and none of: 1) provider repeated		elevated blood pressure
blood pressure, 2) clinic note mentions elevated		at triage
blood pressure/hypertension 3) plan included		
recheck or evaluation of blood pressure, or 4)		
ordering laboratory or other studies to evaluate		
elevated blood pressure		
Delayed Actions on Laboratory Results per	1. Percent of providers with	1. Weekly nurse review of
100 Abnormal Laboratory Results Received 	unread or	all abnormal laboratory
No documented action step for first positive after	unacknowledged	results
30 days:	laboratory results in their	2. Standardized protocols
1. Hgb similar and MCV similar 2 year old $\rightarrow$	EHR inbox for greater than	for handling laboratory
documentation of beginning iron, sending	72 hours	results
Iron studies or family conversation		3. Standing orders for
2. Lead >5 > documentation of family		laboratory results action
conversation on lead remediation or plan to		steps to be completed by
No documented action atom for first positive after		nuise with appropriate
		provider oversight
1 Dositive Conorrhea Chlamydia Synhilis or		
HIV test documentation of antibiotics		
heave or referral to HIV specialist		
2 Positive group A streptococcal throat culture		
with negative rapid group A streptococcal		

	test→documentation of antibiotics begur family conversation	ı or
3.	TSH $\leq$ 0.5 or $\geq$ 4.5 in $\geq$ 1 year old $\rightarrow$ plan	to
	repeat lab values or referral endocrinologist	to

Early detection via screening represents the best opportunity to reduce missed diagnosis of adolescent depression. We will screen patients with the Patient Health Questionnaire 9-item Modified for Adolescents (PHQ-9-M), as it is a validated and highly specific tool (94.7%). Building on work done by [name], a member of the Project Expert Group and others, we will use coaching and learning sessions to ensure appropriate follow-up for identified mental health concerns are in place before practices begin universal screening. The evidence-based tools utilized by the collaborative to improve diagnosis of adolescent depression include patient screening in the waiting room, followed by nurse scoring and flagging. This methodology increased adolescent screening rates to 80-84% in QI interventions at CHAM and in 6 non-affiliated sites, and is a necessary first step to adolescent depression diagnosis.

The missed diagnosis of pediatric elevated blood pressure primary outcome is defined as elevated systolic or diastolic blood pressure for age, gender and height without provider recognition per 100 elevated blood pressures measured in intervention versus control practices. The process measure will assess the percent of children  $\geq$ 3 years old receiving blood pressure measurement at triage, as this is standard of care and an endorsed recommendation by the AAP, but not regularly adhered to in all pediatric clinics. The evidence-based tools implemented by the collaborative to help reduce this diagnostic error will involve triage nurse or EHR flagging of elevated blood pressures for provider recognition and family notification of elevated blood pressures.

The delayed diagnosis of actionable laboratory results primary outcome measure is defined as the number of delayed actions, as defined in Table 2, per 100 abnormal laboratory results received in intervention versus control practices. Abnormal values are defined by pediatric reference texts. Since no standard definition of an actionable laboratory 'delay' currently exists, timeliness of follow-up was determined by expert opinion and discussions with primary care practitioners. Delays are defined as greater than 30 days for action on elevated lead levels or microcytic anemia, or greater than 7 days for action on STI treatment, *streptococcal* pharyngitis treatment or elevated or reduced TSH work-up. The process measure for delayed diagnosis of actionable laboratory results will be the number of providers with laboratory results unread or unacknowledged in their EHR inbox for more than 72 hours. The tools implemented by the collaborative will include standing orders for nurse actions when abnormal test results are received. For example, if a patient has a positive Chlamydia test, the nurse will immediately call the patient and schedule the next available visit for counseling and antibiotics. These interventions are based on successful newborn screening QICs at CHAM and QuIIN, and AHRQ's toolkit for improving office-based testing.

QIC Data Collection and Standardization:

An initial orientation session will teach all practices to identify each of these 3 diagnostic errors via chart review, collect data and reliably enter it into the QuIIN IT system, QIDA. The QIDA system has been used by prior QuIIN projects, is web-based and HIPAA compliant, and QuIIN will take responsibility for data security. QuIIN's project manager has experiencing ensuring accurate and timely data submission for primary care pediatric practices from prior

Practice			
Baseline	QIC Intervention Period		
(One Time Data Collection)	(Monthly Data Collection)		
Missed Adolescent Depression			
50 > 11 year old patient charts who	17 11 year old patient charts who		
visited clinic in prior 6 months.	visited clinic in prior month. Chart		
Chart screened for depression	screened for depression		
diagnosis.	diagnosis.		
Missed Elevated Blood Pressure			
50 2 year old patient charts with	10 2 year old patient charts with		
elevated blood pressure recorded	elevated blood pressure recorded		
at triage. Chart screened for	at triage. Chart screened for		
provider recognition.	provider recognition.		
Delayed Diagnosis of Actionable			
Laboratory Results			
50 patient charts with abnormal	10 patient charts with abnormal		
laboratory results as defined	laboratory results as defined		
above. Chart screened for	above. Chart screened for		
appropriate action within time	appropriate action within time		
guidelines defined above.	guidelines defined above.		
*All charts screened will have the following demographic data recorded: age			

Table 3: QIC Primary Outcome Data Collection for Each

\*All charts screened will have the following demographic data recorded: age, gender and insurance status.

QuIIN QICs.

Practices will collect the primary outcome data by employing EHR based record paper-based review or dependina methods on abilities and interest of local Developing EHRs. data collection tools for both EHR and paper based practices allows for maximum generalizability of lessons learned from this collaborative. These tools will ensure standardized data collection bv disparate were practices and pilot tested with two QuIIN practices. All data collection tools will be pilot tested on paper and beta tested by a

minimum of 2 Expert Group members (always including the QI Advisor). As described below, data will be checked for outliers or abnormal values and feedback given to practices to ensure consistency across practices. Additional data on providers' abilities to recognize abnormal results, either in mental health, blood pressure or laboratory values, will also be collected as this is an important first step in the diagnostic process. These data are described further in the Data collection section below. QIC leadership will use QIDA entered data to disseminate monthly feedback reports with full transparency and QIC benchmarking to intervention practices. Consented core QI team members from each practice will be able to access their team's data. All practices will report demographic data annually, including patient volume, number and training level of physician or physician assistant-level providers, number of nursing and office staff, university-affiliation, EHR availability, presence of trainees, estimated length of time providers take with patients, and prior self-reported work aiming to improve these diagnostic errors.

Table 3 summarizes the primary outcome data each practice will collect and the types of charts they will screen. Numbers of charts are based on power calculations described below and will be a convenience sample. Adolescents with depression will be identified by monthly chart reviews or EHR data summaries when this diagnosis is mentioned in the problem list or in assessment sections of visit notes. Pediatric elevated blood pressures will be identified by flagging blood pressure measurements at triage or pulling reports from EHR systems. Similar to the depression outcome, provider recognition will be identified when this diagnosis is mentioned in the problem list or in assessment sections of visit notes. Finally, abnormal lab results will be tracked by either EHR laboratory summary reports or laboratory management registry tools, such as those found in the AHRQ toolkit for improving office-based testing, and provider recognition will be identified when a diagnosis is mentioned in the problem list, in assessment

sections of visit notes or if medications are prescribed. Intervention practices will also report process outcomes (Table 2).

